Surgical interventions target anatomical obstructions,⁵⁹ but there is little overall evidence to support the efficacy of surgery for OSA.⁶⁰ Furthermore, severe pain and post-operative infection commonly accompany the surgeries, and many surgical patients are dissatisfied.⁶⁰ There have been limited randomized trials of other strategies, e.g., upper airway dilator muscle stimulation,⁶¹ upper airway muscle training,⁶² and acupuncture.^{63,64}

3.3.2. Weight Loss is a common first treatment for OSA. Estimates indicate that AHI is reduced by about 3% for every 1% drop in weight.^{17,18} In a recent meta-analysis, interventions of similar duration and weight loss as proposed resulted in 34% decrease of AHI.¹⁸ Weight loss likely promotes increased upper airway caliber by decreasing upper airway fat deposition and increasing lung volume by decreasing the mechanical load on the chest wall. Upper airway collapsibility has been shown to decrease substantially following weight reduction.

Behavioral weight loss studies typically involve weekly or twice monthly behavioral meetings with weight loss staff^{65,66} and can elicit weight loss of 0.5-1.0 kg/week.⁶⁷⁻⁶⁹ The structure of this treatment⁶⁹⁻⁷² focuses on the following: (1) Goal setting allows participants to establish measurable goals that they can track; study counselors use these goals to assess progress and provide tailored feedback about the rate of weight loss. (2) Self-monitoring⁷⁰ requires daily recording of foods and the kcal and macronutrients (g) in each food item; counselors review the journals to assess adherence to recommendations.⁷² (3) Teaching stimulus control concepts involve creating home and work environments that, for example, are free of cues to overeat.⁶⁹

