3.4. Possible Mechanisms for Improved OSA with Exercise. Although exercise and weight loss have some overlapping mechanisms for reducing OSA, there are rationales for additive effects of exercise and weight loss. Both dependent and independent of body weight changes, exercise may reduce OSA by increasing ventilatory muscle strength, including upper airway musculature. Increased resting ventilatory muscle tone could reduce compliance of the upper airway and, thus, diminish collapsibility. Greater pressure developed by ventilatory muscles may also counteract a tendency for airway obstruction via a more efficient exchange of air.

Particularly in the obese, a decrease in chest wall compliance could reduce the force-generating capacity of inspiratory muscles and predispose one to upper airway collapse due to reduced pressure development. Also, low static lung volumes (e.g., expiratory reserve volume) are associated with apnea and nocturnal oxygen desaturation. Exercise training has been shown to improve respiratory muscle strength in people with respiratory muscle weakness and in sedentary adults.⁸⁹

Chronic exercise may also reduce OSA severity by decreasing fatigability of ventilatory and upper airway muscles.^{90,91} The upper airway (UA) dilator muscles of apneics consist of a greater proportion of fast-twitch muscle fibers compared with those who do not have OSA,⁹² conferring greater fatigability (and possibly progressive loss of force generation during sleep).⁹³ In animals, chronic exercise elicits an oxidative fiber-type shift of the UA dilator muscles,⁹⁴ and chronic low-frequency electrical stimulation induces similar muscle fiber alterations of the genioglossus.⁹⁵ Activation of the UA dilator muscles increases in parallel with increasing exercise intensity.⁹⁶ Similarly, training the UA dilator muscles during wakefulness, either via wind instrument practice or electrical stimulation, has been shown to reduce AHI.^{62,97}

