5.2. Design Overview. Following extensive screening and baseline assessment, overweight/obese veterans with OSA (N=90) will be randomized to one of three 16-week treatments: (1) **Exercise Alone**, consisting of aerobic and resistance exercise (n=30); (2) **Weight Loss Alone** (n=30), with a goal of 10% reduction of body weight; or (3) **Exercise + Weight Loss** (n=30). Before and after the treatments, participants will undergo 5 days/nights of home-based actigraphic and diary-assessed sleep, and 1 night of laboratory polysomnographic (PSG) recording to assess OSA severity. Secondary co-morbidity measures will include body weight/composition, blood pressure, heart rate variability, glucose, insulin, hemoglobin A1c, lipids, and inflammation.

5.3. Volunteer Recruitment and Screening. The study sample will be drawn primarily from the Phoenix VA. There are over 30,000 Phoenix VA veterans who have been diagnosed with OSA. Approximately 50% of patients referred to the Phoenix VA sleep laboratory are cases of suspected OSA who must wait an average of 20 weeks between referral and treatment (usually PAP). Each week, there are about 25 new cases of Phoenix VA veterans. As observed elsewhere,^{11,17} PAP adherence is very low in these patients.

For the present study, several steps will be taken to recruit participants. First, other VA physicians and nurses will be informed about the prevalence, predictors, and consequences of OSA and asked to refer suspected cases to the VA Sleep Laboratory. Second, patients who have been referred to the sleep laboratory for suspected OSA and who appear to meet other inclusion criteria (based on VA medical records) will be sent a letter inviting participant by [name] (**Appendix 3**). If deemed necessary by the IRB, we will acquire HIPAA waiver to review the records and contact these patients, as we have done for other VA studies. Third, once patients are diagnosed with OSA, they will be informed/reminded about the study and that they may still enter the study in the future. We will also recruit veterans by notifying non-VA sleep clinics about the study and via advertisements in VA, ASU, military media, newspapers, and flyers posted throughout the VA and on TV. Recruitment efforts will be structured to reflect the demographics of Phoenix VA veterans.

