5.10. Statistical Analysis. We will first examine univariate and bivariate statistics to determine the distributional characteristics of study variables and to identify potentially relevant background covariates and confounders. For the **Primary Hypothesis and Secondary Hypotheses 1 and 3**, we will use an analysis of covariance (ANCOVA) approach to examine treatment effects on post-intervention (i.e., immediate post-test for Primary Hypothesis and Secondary Hypothesis 3; 3-month follow-up for Secondary Hypothesis 1) outcome values (i.e., AHI scores for Primary Hypothesis and Secondary Hypothesis 1; comorbidity measures for Secondary Hypothesis 3), with treatment as the primary independent variable, and adjusting for baseline outcome value, intervention dose (percentage of sessions attended), baseline outcome value, age, sex,

duration of OSA diagnosis, plus any other relevant covariates. We will test for ordering of treatment means (not adjusted for covariates) via order-restricted tests within the R package flexisoreg. Next, we will test for overall differences among treatment groups on post-treatment AHI values with order-restricted comparisons (isotonic contrasts) of covariate-adjusted means to test for the predicted ordered patterning of the three treatment means. For **Secondary Hypothesis 2**, we will examine the effect of time point (pre- vs. post-treatment) on AHI scores at each treatment level (i.e., test “simple main effects” of time) in the context of a repeated measures ANCOVA. Analyses will be based on an intent-to-treat plan. For each hypothesis, overall alpha will be set at .05, with a Bonferroni correction applied when multiple non-independent tests are conducted. **Missing data** due to dropout or other causes will be addressed with analyses of multiply-imputed datasets generated with SAS PROC MI based on models drawing on all available participant data.

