Mediation Analysis. Possible mediating variables that could explain the reduction in OSA will be evaluated using MacKinnon’s product of coefficients test. Pre-specified potential mediators will include percent of NREM-3 (deep sleep), body weight, trunk body fat percentage, respiratory muscle strength, and upper airway obstruction (FIF₅₀/FEF₅₀). Each potential mediator will be tested in a single mediator model, to include (1) estimating the effect of the intervention on the potential mediator (i.e., α coefficient) by regressing the mediator’s post-intervention value on the intervention group while controlling for the potential mediator’s baseline value; (2) estimating the effect of changes in the mediator on changes in AHI (i.e., β coefficient) by regressing post-intervention AHI on the mediator’s post-intervention value, controlling for treatment group, baseline AHI, and the mediator’s baseline value; and (3) calculating the product of coefficients by multiplying the α and β coefficients. Coefficients will be obtained through linear regression models using SAS PROC GLM. Asymmetric confidence limits based on the distribution of the product of coefficients will be created using the PRODCLIN program; confidence intervals that do not include zero will indicate a significant mediation effect.

5.11. Process evaluation. An independent observer will assess study feasibility, fidelity of protocol delivery, and subject adherence. Participants will also complete a survey of barriers and benefits to study participation.

5.12. Timeline. The study will take 4 years. Equipment purchases will occur in the initial 2 months. With rolling admission, we will strive to schedule waves of ≥ 5 participants. Baseline assessments should begin by the end of Month 2, and baseline assessments of new waves of participants will occur monthly. Data collection is expected to take 44 months. Final analyses and manuscripts preparation will occur during the final 2 months.

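### Testing each mediator alone cannot separate mediation from within-arm correlation with weight change, yet the stated rule can declare such a correlate a significant mediator

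*Combined protocol and SAP*

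**What the plan says.** The Mediation Analysis paragraph of section 5.10 lists five candidates: "Pre-specified potential mediators will include percent of NREM-3 (deep sleep), body weight, trunk body fat percentage, respiratory muscle strength, and upper airway obstruction". It then states: "Each potential mediator will be tested in a single mediator model". The alpha step regresses the post-intervention mediator on treatment group and the mediator's baseline. The beta step regresses post-intervention AHI on the post-intervention mediator, "controlling for treatment group, baseline AHI, and" that mediator's own baseline. PRODCLIN gives the interval for the product of the two coefficients, and "confidence intervals that do not include zero will indicate a significant mediation effect".

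The paragraph describes no model with two mediators, no sensitivity analysis for mediator-outcome confounding and no caveat about correlated mediators. It does not say which contrast among the three arms defines alpha. The main part of section 5.10 says that "overall alpha will be set at .05, with a Bonferroni correction applied when multiple non-independent tests are conducted", without saying whether this covers the five mediators.

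Two background statements bear on the point. Section 3.3.2 reports that "AHI is reduced by about 3% for every 1% drop in weight". Section 3.4 says: "Both dependent and independent of body weight changes, exercise may reduce OSA by increasing ventilatory muscle strength".

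**The concern.** Randomisation protects the alpha step but not the beta step. Within an arm, nobody is randomised to a mediator value. If weight change drives AHI and also correlates with trunk fat or respiratory strength within arms, a model that omits weight credits part of its effect to the other variable. Baseline covariates cannot repair this, because the omitted variable is itself measured after randomisation.

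The protocol makes weight the obvious omitted driver. Two of the five mediators, body weight and trunk fat percentage, both measure adiposity. Section 3.4 expects strength to act partly with and partly apart from weight change, and a strength model without weight cannot separate those routes. The risk is that one weight effect is reported as several mechanisms, or that a weight-independent exercise mechanism is claimed without support.

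**Working it through.** The plan gives no power or error rate for the mediation analysis, so it has no figure to reproduce.

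**Inputs from the documents**
- Design: "veterans with OSA (N=90) will be randomized to one of three 16-week treatments", 30 per arm; with 10% attrition (section 5.9), 27 per arm and 81 in all.
- Weight-loss goal of 10% (section 5.5.2).
- Weight effect: 3% of the baseline AHI of 32.2 per 1% of weight, 0.03 × 32.2 = 0.97 AHI units.
- SD of AHI change: 5 (section 5.9, primary hypothesis) or 12.5 (section 5.9, Secondary Hypothesis 2).

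**Assumptions, not in the documents**
- Within-arm SD of weight change of 4 percentage points.
- Within-arm correlation ρ between proxy and weight change, varied.
- A 1 SD exercise effect on strength.
- A linear model in which only weight affects AHI.
- Contrast for alpha: Exercise + Weight Loss against Exercise Alone for trunk fat, and against Weight Loss Alone for strength.

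**Hand check of the beta step.** For a proxy with no effect of its own, scaled to within-arm SD 1, the omitted-variable formula gives

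β = 0.966 × 4 × ρ = 3.864ρ.

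The model has six coefficients (intercept, two arm terms, baseline AHI, mediator before and after), leaving 81 − 6 = 75 degrees of freedom, so

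SE ≈ √(SD² − β²) / √75.

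- ρ = 0.7, SD 12.5: β = 2.70; SE = √(156.25 − 7.32)/√75 = 1.41; ratio 1.92; chance of significance at two-sided 0.05 about 47%.
- ρ = 0.9, SD 12.5: β = 3.48; SE = 1.39; ratio 2.51; about 70%.
- ρ = 0.2, SD 5: β = 0.77; SE = √(25 − 0.60)/√75 = 0.57; ratio 1.35; about 27%.
- ρ = 0.5, SD 12.5: β = 1.93; SE = 1.43; ratio 1.35; about 27%.

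**Simulation of the whole procedure** (1,000 trials per setting; a Monte Carlo product interval in place of PRODCLIN). Share of trials in which the null proxy is declared a mediator:

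| Proxy and contrast | \|ρ\| | AHI-change SD 5 | AHI-change SD 12.5 |
|---|---|---|---|
| Trunk fat, against Exercise Alone | 0.1 | 1% | 1% |
| | 0.3 | 38% | 9% |
| | 0.5 | 94% | 29% |
| | 0.7 | 99.9% | 50% |
| | 0.9 | 100% | 71% |
| Strength, against Weight Loss Alone | 0 | 6% | 6% |
| | 0.1 | 12% | 8% |
| | 0.2 | 28% | 11% |
| | 0.3 | 52% | 15% |
| | 0.5 | 90% | 28% |

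Repeat simulations agree to within a few points, which is why the conclusion uses rounded ranges. The hand figures match where the alpha effect is easily detected. At low ρ the trunk-fat rates are lower than β alone implies, because the product interval also needs a detectable alpha.

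**Limits of the effect**
- A proxy shifted 2.5 SD between arms but uncorrelated with weight within arms is flagged in 6%, because arm is in the beta model.
- Against Weight Loss Alone, where both arms share the weight goal, a weight proxy with no exercise effect of its own is flagged in at most about 5%.
- With weight-change SD of 3 to 5 points and ρ = 0.7-0.9, the trunk-fat range is 96-100% (SD 5) and 32-88% (SD 12.5).
- With weight-change SD of 2.5, trunk fat at 0.8 is flagged in 96% and 30%, and strength at 0.4 in 43% and 10%.

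**With body weight in the same beta regression**, the null proxy is flagged at close to the nominal rate, no more than about 8% in any run.

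**The case against.** Several points against the concern stand. A reader might infer that anything moving with weight loss will be declared a mediator. The documents do not support that: the beta step controls for treatment group, so movement between arms alone does no harm. A reader might also infer that trunk fat and strength have no effect of their own. That is the premise of the simulation, not a fact. Section 3.1 describes torso fat loading the upper airway, and section 3.4 gives ventilatory strength a mechanism. Trunk fat may be how weight loss works, so adjusting it for weight would ask a different question.

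The largest figures also need a favourable setting. At SD 5, weight explains (0.966 × 4)²/25 = 60% of within-arm variance in AHI change. At the SD of 13 observed in the previous study (section 5.9), it explains 14.93/169 = 9%, so the 12.5 column is closer to observed data.

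Mediation is no stated hypothesis, and the mediators are called possible or potential. The randomised arms address exercise benefit more directly.

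Bonferroni helps only partly. At 0.05/5 and SD 12.5, strength is flagged in 2-10% and trunk fat in 17-48%, against a nominal 1%. It limits chance error but leaves a biased coefficient biased. Nor does calling a mediator potential soften a rule that says an interval excluding zero will indicate mediation.

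**Conclusion.** The concern holds in a limited form. Single-mediator models cannot distinguish a mediator from a within-arm correlate of weight change, and the stated rule can declare such a correlate significant. Under the assumptions above, the rate for a null trunk-fat proxy at correlation 0.6-0.9 is about 99-100% (AHI-change SD 5) or 40-70% (SD 12.5). For a null strength proxy at 0.2-0.5 it is about 26-91% or 8-30%.

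These sizes rest on correlations and a weight-change SD that the documents do not give. High correlation is plausible for trunk fat, since it and weight both measure adiposity. For strength it is uncertain, and at 0.1-0.2 with SD 12.5 the inflation is small. The exposure is confined to claims about mechanism; the primary and secondary treatment comparisons are unaffected.

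**What to change.** Amend the Mediation Analysis paragraph of section 5.10 as follows.

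1. For respiratory muscle strength, airway obstruction and NREM-3, add baseline and post-intervention body weight to the beta regression. Base any claim of a weight-independent mechanism on that model.
2. Fix body weight in advance as the adiposity measure. Allowing trunk fat in that role is not equivalent: if weight is the true driver, adjusting for trunk fat still left strength flagged in up to 71% of simulated trials (SD 5, trunk fat-weight correlation 0.6, strength-weight 0.5).
3. Report body weight and trunk fat percentage as two measures of one adiposity pathway, not as separate mediators.
4. Describe single-mediator results as unable to distinguish mediation from correlation with weight change, and withdraw the rule that their intervals indicate a significant mediation effect.

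The cost is SAP wording and a few regressions on data already collected. Intervals widen somewhat: the standard error grows by about 1/√(1 − ρ²), a factor of 1.02 at ρ = 0.2 and 1.15 at ρ = 0.5. With strength and weight entered together, power to detect weight as a mediator falls from about 80-84% to about 69-77% at SD 12.5 and is unchanged at SD 5. Entering weight and trunk fat together would cost far more (from 80% to 52% at ρ = 0.7 and 26% at ρ = 0.9, SD 12.5), so that model is not proposed.

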5.5. Treatment Randomization, Instructions, Adherence Strategies. Following baseline, participants will be randomized to one of three 16-wk treatments: (1) **Exercise Alone** (n=30) (**5.5.1**); (2) **Weight Loss Alone** (n=30) (**5.5.2**); or (3) **Exercise + Weight Loss** (n=30) (**5.5.3**). Randomization will be stratified by age (< vs. ≥ 40), sex, and severity of screening AHI (10-25 or > 25) in blocks of 6, using a computer-generated list.

The duration of the intervention was chosen so that there would be sufficient time to detect chronic adaptations to the interventions without placing undue burden on the participants. Sixteen weeks is sufficient time to detect chronic exercise benefits¹⁴ and to achieve the targeted weight loss using the moderately challenging proposed procedures. Following randomization, treatment expectancy for changes in OSA severity, sleep quality, daytime sleepiness, mood, and health will be assessed via 5-point Likert scales.

Lifestyle Activity and Eating. Because lifestyle changes could mask the effects of the experimental exercise and weight loss, participants will be asked to maintain their normal activity and eating habits, except as prescribed for the study. In our previous trial, such requests were followed, as evidenced by the lack of weight loss¹⁹ and the proposed monitoring methods.

To monitor changes in unsupervised physical activity, participants will wear a waist accelerometer from baseline through the post-intervention assessment (except during experimental exercise). This device has been validated against energy expenditure estimated with oxygen consumption and doubly labeled water. It records daily steps and time spent in light, moderate, and vigorous activity. Data will be analyzed in 2-wk bins.

Food intake will be assessed with the Automated Self-Administered 24-hr diet recall (ASA24) (<http://riskfactor.cancer.gov/tools/instruments/asa24/>), to be completed twice during baseline and during Weeks 8 and 16 of treatment. The recall is among the highest quality with the least bias and subject burden.

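### The mediator-to-AHI regression is observational, yet it omits age, sex and duration of OSA diagnosis, which the outcome ANCOVA already uses: a minor gap that is cheap to close

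*Combined protocol and SAP*

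**What the plan says.** The Mediation Analysis paragraph of section 5.10 names five candidate mediators: "percent of NREM-3 (deep sleep), body weight, trunk body fat percentage, respiratory muscle strength, and upper airway obstruction". Each is tested alone, in two regressions.

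- **Alpha:** the post-intervention mediator is regressed "on the intervention group while controlling for the potential mediator’s baseline value".
- **Beta:** post-intervention AHI is regressed on the post-intervention mediator, "controlling for treatment group, baseline AHI, and the mediator’s baseline value".

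Alpha and beta are multiplied and an asymmetric interval is formed with PRODCLIN. The decision rule is that "confidence intervals that do not include zero will indicate a significant mediation effect".

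The ANCOVA for the Primary Hypothesis and Secondary Hypotheses 1 and 3, in the same section, has a longer list. It is specified as "adjusting for baseline outcome value, intervention dose (percentage of sessions attended), baseline outcome value, age, sex", followed by "duration of OSA diagnosis, plus any other relevant covariates". Section 5.10 also opens with a descriptive step, in part "to identify potentially relevant background covariates and confounders". The mediation paragraph does not refer back to that step or to the ANCOVA list. It states no assumption about mediator–outcome confounding.

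**The concern.** Randomisation protects alpha, because alpha compares arms. It does not protect beta, which relates two variables that both arise after randomisation. A baseline characteristic that drives both the mediator's movement and AHI's movement makes beta non-zero even when the mediator does nothing. Where treatment also moves the mediator, the product interval can then exclude zero.

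The plan therefore adjusts for age, sex and OSA duration where randomisation already balances them in expectation, and leaves them out of the one coefficient where background confounding can create a result. The documents themselves treat age and sex as relevant: section 3.1 lists both as OSA risk factors, and section 5.5 says "Randomization will be stratified by age (< vs. ≥ 40), sex, and severity of screening AHI". At stake is the explanation offered for any AHI reduction, not the test of whether AHI fell.

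**Working it through.** **1. The covariate lists side by side.**

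| Covariate | Outcome ANCOVA | Beta regression | Alpha regression |
|---|---|---|---|
| Treatment | yes | yes | yes |
| Baseline AHI | yes (AHI outcomes) | yes | no |
| Baseline mediator | no | yes | yes |
| Age, sex, OSA duration | yes | no | no |
| Session attendance | yes | no | no |

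The plan gives no power or error figure for the mediation analysis, so there is none to reproduce.

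**2. Inputs for an illustration.** Section 5.9 gives 30 per arm and 10% attrition, hence 27 per arm and 81 completers. The rest is assumed:
- the true effect of mediator on AHI is zero;
- treatment shifts the mediator by 1 residual SD in the contrast tested;
- one omitted baseline factor has correlation r with both mediator and AHI, after arm and baseline values are accounted for.

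The documents do not give r, so a range is shown.

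**3. Closed-form approximation.** With unit residual variances:
- spurious beta = r²;
- SE(beta) ≈ √[(1 − r⁴)/75], where 75 = 81 − 6 fitted coefficients;
- SE(alpha) = √(2/27) = 0.272, so z = 1/0.272 = 3.67 and the chance that alpha is significant is about 0.957;
- false mediation ≈ P(beta significant) × 0.957, both tests two-sided at 0.05.

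At r = 0.3, beta = 0.09, SE = 0.115 and z = 0.78. Beta is significant with probability 0.123, and 0.123 × 0.957 = 0.117.

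**4. Results, with simulation (4,000 trials per r, both coefficients significant).**

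| r | Spurious beta | Closed form | Simulated, as planned | Simulated, factor in both models |
|---|---|---|---|---|
| 0 | 0 | 4.8% | 4.6% | 4.4% |
| 0.2 | 0.04 | 6.1% | 6.1% | 4.9% |
| 0.3 | 0.09 | 11.7% | 11.2% | 5.2% |
| 0.4 | 0.16 | 27.7% | 26.6% | 5.1% |
| 0.5 | 0.25 | 58.2% | 57.2% | 4.3% |

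A repeat simulation gave about 13% at r = 0.3.

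**5. Does the shortcut matter?** Joint significance stands in above for the PRODCLIN interval. A separate simulation used distribution-of-product intervals, a mediator shift of 1.5 residual SD, and a shared cause correlated 0.3 with both baselines. With the shared cause explaining 5%, 10%, 20% and 30% of residual variance in both variables (r = √0.05 = 0.22, then 0.32, 0.45 and 0.55), false mediation was 7%, 14%, 35% and 66%. With the factor included it was 5–6%. The pattern is the same.

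**6. When the arms do not differ on the mediator.** The multiplier 0.957 becomes about 0.05. At r = 0.5 this gives 0.609 × 0.05 = 3.0%. Simulation of Exercise + Weight Loss against Weight Loss Alone, with equal weight change in both, gave 0.2%, 0.6%, 1.3% and 2.6% at r = 0.2, 0.3, 0.4 and 0.5.

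**The case against.** **The simulated factor is not age, sex or duration.** Section 3.1 says age and sex are linked to having OSA, which is a statement about level, and the baseline AHI and baseline mediator terms already absorb much of any level effect. Nothing in the documents shows that these variables predict change in both quantities. Stratification concerns balance between arms, not mediator–outcome confounding. This stands, and it is why no size can be claimed. The omission from the stated model remains.

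**Alpha need not be non-zero.** There is no untreated arm, and sections 5.5.2 and 5.5.3 give both diet arms the same weight-loss protocol. For Exercise + Weight Loss against Weight Loss Alone, the body-weight alpha may be near zero and the risk small (step 6). This stands. The exposure is mainly body weight and trunk fat in the diet arms against Exercise Alone. The paragraph does not say which contrast is tested.

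**The opening screening step may cover it.** In part: it shows intent, but nothing carries it into the mediation models, which name their own covariates.

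**Three covariates do not remove confounding.** Correct. Adherence, the other mediators and unmeasured causes remain. The return to about 5% in step 4 assumes that the whole shared cause is measured and included.

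A reader might also infer that the shorter alpha model is biased or inconsistent with the ANCOVA. It is not: treatment is randomised, and the two models have different outcomes.

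**Conclusion.** The point holds as a minor improvement. Beta is observational, its stated covariate list omits three baseline variables that the same section uses for the outcome, and the decision rule reads a non-zero product as mediation without qualification.

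False mediation requires two conditions: an omitted variable predicts both changes beyond baseline, and treatment moves the mediator in the contrast tested. Given both, the illustrative rate is negligibly raised at r = 0.2 (about 6%), about 11–13% at r = 0.3, and high only for strong shared causes.

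Two stronger readings are tempting. One is that the mediation findings will be wrong as planned, at rates such as 27% or 57%. Those figures need a factor explaining 16% to 25% of residual variance (0.4² to 0.5²) in both changes, and the documents offer no evidence of that. The other is that the risk applies equally to all five mediators. It depends on treatment separating the arms on each one, which the documents do not establish for deep sleep, muscle strength or airway obstruction.

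The analysis is explanatory. The primary and secondary hypothesis tests do not depend on it.

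**What to change.** In the Mediation Analysis paragraph of section 5.10:

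1. Add baseline age, sex and duration of OSA diagnosis to the beta regression for every mediator.
2. Add the same three to the alpha regression, only so that both regressions use one covariate set, not because alpha is biased.
3. Do not carry over session attendance from the ANCOVA; it is measured after randomisation.
4. State that beta remains observational, and that an interval excluding zero is evidence consistent with mediation on the assumption of no unmeasured mediator–outcome confounding.

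The cost is one or two sentences and about 3 degrees of freedom out of about 75. Age and sex are known at randomisation. Collection of OSA duration is only implied by its place in the ANCOVA: no measurement section describes it, and section 5.3.1.2 also admits people identified as high risk by questionnaire. It should enter the mediation models exactly as recorded for the ANCOVA. The change should be made before outcome data are examined, so that the covariates are not chosen in the light of results.
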